11.3 Methods of analysis

Reactogenicity following immunisations will be presented as the number and percentage of participants self-reporting local reactions (pain; tenderness, redness; swelling at or near the injection site) and systemic reactions (fever, nausea/vomiting, headache, fatigue/malaise, myalgia), and the severity of

these reactions (mild, moderate, severe, life-threatening or fatal). Reactogenicity data will be presented separately by group and time point.

For immunogenicity, antibody levels will be presented as geometric mean titres (GMT) with 95% confidence intervals. Changes from baseline will be expressed as geometric mean fold ratios (GMFR), calculated as the ratio of the post-booster GMT to the baseline GMT. Seroresponse will be defined as a ≥ 4 -fold rise in post-booster antibody levels compared to baseline (or ≥ 2 -fold rise if the baseline (pre-booster) antibody level was ≥ 200 BAU/ml). To assess the non-inferiority of the fractional dose compared with the standard dose, comparisons will be based on the difference in percentage of participants with seroresponse. Using a non-inferiority margin of -10% (fractional-dose minus standard dose), non-inferiority will be declared if the lower limit of the 95% confidence interval around the difference in percentages is greater than -10%, where confidence intervals are calculated using Score-based methods (14)

Analyses will be performed using Stata software (15). Detailed methodology will be outlined in a separate Statistical Analysis Plan.

Primary outcome (All samples at all timepoints)

The binding IgG data using the Euroimmun S1 IgG ELISA kits will be reported as relative units/ml (RU/ml) as per manufacturer's instructions. A result of < 8 RU/ml: negative (IgG Antibodies for SARS-CoV-2 are not detected), ≥ 8 to < 11 RU/ml: borderline (IgG antibodies is indeterminate/equivocal with this sample), ≥ 11 RU/ml: positive (IgG antibodies for SARS-CoV-2 are detected). Conversion to binding antibody units (BAU/ml) will also be done using the WHO reference serum from NIBSC, UK. Data will be presented as geometric mean titres and 95% confidence intervals.

Analysis comparing fractional and standard dose groups will be based on seroresponse rate (SRR) at 28 days post study vaccine, defined as:

- ≥ 4 -fold rise in GMCs at 28 days post study vaccine from baseline among subjects with no pre-dose (< 200 BAU/ml) detectable titres
- ≥ 2 -fold rise in GMCs at 28 days post study vaccine among subjects with baseline titre of > 200 BAU/ml pre-booster

Secondary outcomes

Functional antibody (all samples at all timepoints) – for the C-PASS assay (sVNT), data is reported as percentage (%) inhibition by neutralising antibodies using the manufacturer's instructions. A $< 30\%$ inhibition is considered negative while $\geq 30\%$ inhibition is considered positive. Data will be presented as mean and standard deviation.

Neutralizing assay (20% subset of samples at all timepoints) – Data will be reported as endpoint titre calculated using the Reed/Muench method (16). A titre of 10 reflects undetectable neutralizing activity.

Cellular immunity: (on a 40% subset at three timepoints – baseline, 1 month and 12 months)

Quantiferon COVID IFN γ release assay – Levels of IFN γ will be reported in IU/ml according to manufacturer's instructions. Data will be reported as GMC and 95% confidence intervals.

IFN γ Elispot – The number of IFN γ producing cells/million PBMCs will be reported using means and 95% confidence intervals.

Intracellular cytokine staining – The data will be reported as frequency (%) of cytokine-expressing T cells (e.g. total T cells, CD4 T cells, CD8 T cells). Cytokines such as IFN γ (Th1) and IL-5 (Th2) will be measured as a minimum. This will be presented as means and 95% confidence intervals.

Multiplex cytokine assays – A 10-plex panel of cytokines will be measured in supernatants from the Elispot studies. Levels of cytokine concentrations will be reported in pg/ml and data presented as GMC and 95% confidence intervals.

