	
 To assess the rate and severity of reactogenicity within one-week post-booster for each group (Timepoint – 7 days post vaccination) 
Secondary objectives - (timepoint –12 months)
 
 To compare the duration of immunity, both humoral and cellular, over 12 months for fractional vs standard booster doses of the vaccines listed. To evaluate the different priming capacities of Pfizer and AstraZeneca vaccines. To evaluate the safety of the booster dose regimens.
OUTCOMES AND OUTCOME MEASURES	
Outcomes:
 
 Reactogenicity will be measured using the accepted standardised method for evaluation of systemic and local side effects following vaccination using a structured questionnaire for seven days post-vaccination. All moderate or severe reactions will be reviewed by study staff. All solicited adverse events (AE) will be collected for 7 days, all unsolicited AE will be collected for 28 days, and all medically attended AE will be collected for 3 months. SAE will be collected throughout the follow up period of 12 months. Adverse events of special interest will be categorised as per CEPI guidelines (1) Antibodies (binding and functional) and cellular immune responses will be measured (see outcome measures for details) 
Reactogenicity
 
 Reactogenicity will be measured by recording the following parameters: 
 Local reaction - pain, tenderness, erythema/redness, induration/swelling Systemic – Nausea/vomiting, headache, fatigue/malaise/myalgia, arthralgia 
Immunology endpoints
 
Binding antibody – These will be evaluated using the commercial Euroimmun S1 IgG ELISA on serum collected at 4 timepoints (baseline, 28 days, 6 months, and 12 months). For all subjects, the 28 days post-vaccination sample will be assayed within four weeks of collection.
 
Functional antibody – All samples will be assayed using the GenScript cPass SARS-CoV-2 Neutralization Antibody detection kit for both WT and Delta variant RBD antigen.
 
Neutralizing antibody - A fraction of samples (20%) will be assessed using a SARS-CoV-2 assay undertaken at the PDI, Melbourne. Testing will be at 4 timepoints for Wuhan strain and 2 Variants of Concern.

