3.2 Outcomes

3.2.1 Primary outcomes

Immune response

Binding antibody – These will be evaluated using the commercial Euroimmun S1 IgG ELISA on all serum samples collected at 4 timepoints (baseline, 28 days, 6 months, and 12 months). Assays for all subjects will be completed within 4 weeks of sample collection. For subjects who receive a fractional dose, assays on the 28 days post-vaccination sample will be performed within two weeks of collection and reviewed by the DSMB.

Reactogenicity

Reactogenicity will be measured using the accepted standardised method to evaluate systemic and local side effects following vaccination using a structured questionnaire for days post-vaccination as outlined in Table 1 below.

Table 1. Grading system for evaluation of systemic and local side effects following vaccination (11).

Local Reaction to Injectable Product				
	Mild (Grade 1)	Moderate (Grade 2)	Severe (Grade 3)	Potentially Life Threatening (Grade 4)
Pain	Does not interfere with activity	Repeated use of nonnarcotic pain reliever >24 hours or interferes with activity	Any use of narcotic pain reliever or prevents daily activity	ER visit or hospitalization
Tenderness	Mild discomfort to touch	Discomfort with movement	Significant discomfort at rest	ER visit or hospitalization
Erythema/redness ^a	2.5 – 5 cm	5.1 – 10 cm	>10 cm	Necrosis or exfoliative dermatitis
Induration/swelling ^b	2.5 – 5 cm and does not interfere with activity	5.1 – 10 cm or interferes with activity	>10 cm or prevents daily activity	Necrosis

^a The measurement should be recorded as a continuous variable in addition to grading the measured local reaction at the greatest single diameter.
 
^b Induration/swelling should be evaluated and graded using the functional scale as well as the actual measurement.
				
Systemic (General)				
	Mild (Grade 1)	Moderate (Grade 2)	Severe (Grade 3)	Potentially Life Threatening (Grade 4)
Fever (°C) Oral or axillary temperature	38.0 – 38.4	38.5 – 38.9	39.0 – 40	>40
Nausea/vomiting	No interference with activity or 1 – 2 episodes /24 hours	Some interference with activity or >2 episodes/24 hours	Prevents daily activity, or requires outpatient IV hydration	ER visit or hospitalization for hypotensive shock
Headache	No interference with activity	Repeated use of nonnarcotic pain reliever >24 hours or some	Significant; any use of narcotic pain reliever or prevents daily activity	ER visit or hospitalization

		interference with activity		

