Fatigue/Malaise	No interference with activity	Some interference with activity	Significant; prevents daily activity	ER visit or hospitalization
Myalgia (muscle pain)	No interference with activity	Some interference with activity	Significant; prevents daily activity	ER visit or hospitalization
Arthralgia (joint stiffness)	No interference with activity	Some interference with activity	Significant; prevents daily activity	ER visit or hospitalization
In addition, appearance of the following potential signs of myocarditis/pericarditis will prompt referral for cardiology evaluation: Chest pain, dyspnoea, painful breathing, palpitations, or syncope.				

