9.1 Data management

9.1.1 Data generation (source data)

Source documents are all documents used by the investigator that relate to the participant's medical history, that verify the existence of the participant, the inclusion and exclusion criteria, and all records covering the participant's participation in the study. They include but are not limited to

laboratory reports, memoranda, vaccination records, hospital records, and participant files. The site principal investigator is responsible for maintaining source documents.

An electronic CRF (eCRF) will be completed for all recruited participants.

In this study, the following types of data will be collected:

- Identifying personal information (contact details, dates of birth, home address and telephone contact and gender)
- Sensitive information, including health data (dates of COVID-19 vaccinations, medical history, primary COVID vaccine (Pfizer-BioNTech (BNT162b2, or *Comirnaty*®), AstraZeneca (ChAdOx1-S, or *Vaxzevria*®)); intervention vaccine (Pfizer-BioNTech (NT162b2, or *Comirnaty*®), Moderna (mRNA-1273, or *Spikevax*®))
- Reactogenicity information (pain, tenderness, erythema/redness, induration/swelling, fever, nausea/vomiting, headache, fatigue/malaise, myalgia, arthralgia)
- Adverse events and serious adverse events
- Biological information (blood sample, immunologic assay results, including binding antibodies, functional antibodies, neutralizing antibodies, cellular immunity)

Source Document Plan

The source documents for this study include: COVID-19 vaccination details, date of birth, and sex); questionnaires completed by the participant and researcher (MCRI's eCRF).

A Source Document Plan will be maintained to document the source (i.e., original recording) for each data discrete item/category of items collected for the study. This Source Document Plan, signed and dated by the Principal Investigator, will be prepared before recruitment of the first participant and filed in the site's Investigator Site File.

9.1.2 Data capture methods and data use, storage, access, and disclosure during the trial

Data collection methods

Data capture and entry will be electronic. Data for this study will be collected and entered using electronic data collection forms, completed by authorised study staff and participants where applicable.

The following licensed research data collection tools will be used:

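### Section 11.3 omits arthralgia from the systemic reactions that make up a primary outcome; it also gives no fractional-minus-standard estimate of reactogenicity, which would be a cheap addition

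*Combined protocol and SAP*

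**What the plan says.** Section 3.2.1 places reactogenicity among the primary outcomes, measured "using a structured questionnaire for days post-vaccination as outlined in Table 1 below". (The number of days is absent from that sentence as supplied; the synopsis and Section 3.2.2 give seven.) Table 1 grades four local reactions and six systemic ones. The systemic rows run from fever ("Oral or axillary temperature") to "Arthralgia (joint stiffness").

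Three other places list the systemic symptoms:

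- Section 9.1.1, data to be collected: "fever, nausea/vomiting, headache, fatigue/malaise, myalgia, arthralgia".
- Synopsis, outcome measures: "Nausea/vomiting, headache, fatigue/malaise/myalgia, arthralgia".
- Section 11.3, analysis: "systemic reactions (fever, nausea/vomiting, headache, fatigue/malaise, myalgia"), where the bracket closes after myalgia.

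Section 11.3 reports counts and percentages, plus the severity of "these reactions (mild, moderate, severe, life-threatening or fatal"). It then states: "Reactogenicity data will be presented separately by group and time point". Its only fractional-minus-standard contrast is the difference in seroresponse. Detailed methods are left to a separate SAP, which is not among the documents supplied.

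The reactogenicity objective, in the synopsis and in Section 3.1.1, is to assess rate and severity within each group or schedule. Section 11.1 sizes this outcome on the precision of one group's percentage.

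**The concern.** Two matters of different weight arise.

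**Symptom list.** The list in Section 11.3 is closed: it has no wording such as for example or including. A programmer working from it would report five systemic symptoms, while one working from Table 1 would report six. Arthralgia would be solicited, graded and entered for every participant, then left out of the reported results of a primary outcome. If a summary of any systemic reaction is built on the Section 11.3 list, a participant whose only systemic symptom was arthralgia would count as having none. The synopsis has a different gap, so the protocol carries three systemic lists that disagree.

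**Dose contrast.** The title frames reactogenicity, along with immunogenicity and safety, as standard versus fractional dose. Section 4.2 gives fewer moderate reactions as the advantage of the fractional dose to the individual, and Section 2.3.2 raises the prospect of less reactogenicity. Section 11.3 plans no estimate of that reduction. Readers would be left to compare group percentages by eye. The only precision figure the protocol gives them is for a single group.

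**Working it through.** **1. The lists side by side**

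| Place | Systemic symptoms | Missing against Table 1 |
|---|---|---|
| Section 3.2.1, Table 1 | 6 | none |
| Section 9.1.1 | 6 | none |
| Synopsis, outcome measures | all but fever (fatigue, malaise and myalgia run together) | fever |
| Section 11.3 | 5 | arthralgia |

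All four places carry the same four local reactions. Table 1 therefore has 4 + 6 = 10 solicited symptoms and Section 11.3 has 4 + 5 = 9. Section 11.3 omits 1 of 6 systemic symptoms and 1 of 10 overall.

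On severity, Table 1 stops at Grade 4, potentially life threatening, and Section 11.3 adds a fatal level.

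**2. The plan's own precision figure**

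Inputs from Section 11.1: rate p = 50%, n = 100 in one group.

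Half-width = 1.96 × √(p(1 − p)/n) = 1.96 × √(0.25/100) = 9.8 points. The stated 9.8 reproduces.

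**3. Precision of a fractional-minus-standard difference**

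The formula, for equal rates in the two arms, is half-width = 1.96 × √(2p(1 − p)/n), with n per arm.

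- One priming/booster pair, 100 v 100, p = 50%: 1.96 × √(2 × 0.25/100) = 13.86 points.
- One booster product over both priming vaccines, 200 v 200, p = 50%: 1.96 × √(2 × 0.25/200) = 9.80 points, unstratified.

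The documents give no rate for grade 2 or higher reactions. The rates of 10%, 20% and 30% below are assumptions. Half-widths are in points; the score columns use Newcombe's hybrid score interval at equal observed rates.

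| Rate in both arms | Wald, 100 v 100 | Score, 100 v 100 | Wald, 200 v 200 | Score, 200 v 200 |
|---|---|---|---|---|
| 10% (assumed) | 8.32 | 8.68 | 5.88 | 6.02 |
| 20% (assumed) | 11.09 | 11.10 | 7.84 | 7.85 |
| 30% (assumed) | 12.70 | 12.55 | 8.98 | 8.93 |
| 50% (Section 11.1) | 13.86 | 13.60 | 9.80 | 9.71 |

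The choice of interval matters little here. Restoring arthralgia changes no sample-size figure.

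**The case against.** **On the list.** Arthralgia is named in Table 1, the synopsis and Section 9.1.1, so the intent is plain and the data will exist. The separate SAP may already carry the full list. Section 11.3 also defines no composite of any systemic reaction; read as a symptom-by-symptom table, the omission costs one row. This limits the consequence but does not remove the conflict, because the protocol's own lists still disagree on a primary outcome. Whether a composite is intended is open: the 50% in Section 11.1 for local or systemic reactions suggests one, but Section 11.3 does not define it.

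A reader might infer that the systemic reaction rate will be understated by some definite amount. The documents do not support that, since they give neither an arthralgia rate nor the share of participants with arthralgia as their only systemic symptom. A reader might also take the fatal label as an error of classification. It is an extra category that will probably be empty, and it regrades no reaction.

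**On the contrast.** A reader might infer that by-group reporting fails the primary objective. It does not. The antibody objective is to assess and compare, while the reactogenicity objective is only to assess within each group. Objective, sample size and analysis agree with one another. Nor does Section 11.1 offer its 9.8 points as the precision of a difference. A crude difference can be derived from the planned counts, and the separate SAP may specify one. All of this stands, and it makes the contrast an improvement and not a correction.

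**Conclusion.** The symptom list in Section 11.3 is wrong as written: it omits arthralgia, which the primary outcome grades and the study collects. The synopsis separately omits fever. The size in terms of content is 1 of 6 systemic symptoms in each case; the size in terms of results is unknown.

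The missing dose contrast is a gap worth filling at low cost, not a contradiction. At 50% in both arms, with 100 evaluable participants per group, its 95% half-width would be about 13.9 points per priming/booster pair and about 9.8 per booster product. The second figure is unstratified and equals the single-group figure only because n doubles. The overall priority is low, since both changes are small and neither affects the design.

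**What to change.** **Wording.** Add arthralgia to the systemic list in Section 11.3 and fever to the synopsis list, so that both match Table 1 and Section 9.1.1. As a tidy-up only, align the severity labels in Section 11.3 with Table 1.

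**Optional addition to Section 11.3.** Report, as estimation without a hypothesis test, the fractional-minus-standard risk difference with a 95% confidence interval for any, and for grade 2 or higher, local and systemic reactions within 7 days:

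- For each of the four priming/booster pairs, use the score-based interval for two independent proportions that Section 11.3 already cites for seroresponse (taken here as Newcombe's).
- For one estimate per booster product, name a stratified method over priming vaccine and age, the randomisation factors in Section 6. Examples are a Mantel-Haenszel risk difference or a stratified Miettinen-Nurminen score interval. The cited method for two independent proportions does not cover this case.

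If the separate SAP already does this, a cross-reference is enough.

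**Cost.** A few words in two places and one extra table of 2 reaction types × 2 cut-offs × (4 pairs + 2 products) = 24 estimates. No new data, visits or participants are needed. The drawback is that the per-pair intervals will be wide.

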11.4 Interim Analyses

We will conduct an interim analysis of the antibody responses after one month to ensure that the responses in the fractional dose groups are adequate. This will be assessed on both individual and group levels by the DSMB. If fractional dose responses are considered inadequate an appropriate rescue strategy will be developed, probably involving a single dose of the vaccine in question at 3 months. If the fractional dose is considered inadequate this information will be made public and shared specifically with WHO and other groups working in the field. In addition, an analysis will be undertaken once all data are collected for the 6 months analysis to review the potential need for policy changes. All such analyses will be undertaken by the trial statistician, [name].

12 ETHICS AND DISSEMINATION

12.1 Research Ethics Approval & Local Governance Authorisation

This protocol, the informed consent document, and any subsequent amendments will be reviewed and approved by the human research ethics committee (HREC) before the research. A letter of protocol approval by HREC will be obtained before the commencement of the trial and approval for other trial documents requiring HREC review.

12.2 Amendments to the protocol

This trial will be conducted in compliance with the current version of the protocol. Any change to the protocol document or Informed Consent Form that affects the scientific intent, trial design, participant safety, or may affect a participant's willingness to continue participation in the trial is considered an amendment and therefore will be written and filed as an amendment to this protocol and/or informed consent form. All such amendments will be submitted to the HREC for approval before being implemented.

12.3 Protocol Deviations and Serious Breaches

All protocol deviations will be recorded in the participant record (source document) and on the CRF and must be reported to the Site Principal Investigator, who will assess for seriousness.

Those deviations deemed to affect to a significant degree the rights of a trial participant or the reliability and robustness of the data generated in the clinical trial will be reported as serious breaches. Reporting will be done promptly (Site Principal Investigator to report to the Sponsor-Investigator within 72 hours and to the Site RGO within seven days; Sponsor-Investigator to review and submit to the approving HREC within seven days).

Where non-compliance significantly affects human participant protection or reliability of results, a root cause analysis will be undertaken, and a corrective and preventative action plan prepared.

Where protocol deviations or serious breaches identify protocol-related issues, the protocol will be reviewed and, where indicated, amended.

13 CONFIDENTIALITY

Participant confidentiality is strictly held in trust by the participating investigators, research staff, and the sponsoring institution and their agents. This confidentiality is extended to cover the testing of biological samples and genetic tests in addition to the clinical information relating to participating participants.

The trial protocol, documentation, data, and all other information generated will be held in strict confidence. No information concerning the trial, or the data will be released to any unauthorised third party without the prior written approval of the sponsoring institution. Authorised representatives of the sponsoring institution may inspect all documents and records required to be maintained by the Investigator, including but not limited to medical records (office, clinic, or hospital) and pharmacy records for the participants in this trial. The clinical trial site will permit access to such records.

All laboratory specimens, evaluation forms, reports, and other records that leave the site will be identified only by the Participant Identification Number (SID) to maintain participant confidentiality.

Clinical information will not be released without the participant's written permission, except as necessary for monitoring by HREC or regulatory agencies.

